#### 14.6 Grading Severity of Events

The Division of AIDS Table for Grading the Severity of Adult and Pediatric Adverse Events, Version 2.1, March 2017 will be the primary tools for grading adverse events for this protocol.

#### 14.7 Pregnancy and Pregnancy Outcomes

Participation in this study requires taking a Pregnancy Category B medication outside of routine clinical care; therefore only women not intending to become pregnant will be enrolled into this study. The duration of medication dosing is short (5 days before each sampling visit) and scheduled during the early phases of the menstrual cycle (pre-ovulation); therefore the risk of unintentional *in utero* drug exposure is low. Women will be tested at screening using a serum pregnancy test (human chorionic gonadotropin; hCG) and immediately prior to enrollment and each sampling visit using a urine pregnancy test. They will be required to use at least 1 pregnancy prevention strategy during their participation in the study. These may include abstinence for 3 months preceding; monogamy with a vasectomized cisgender male or a cisgender female partner; condoms with spermicide; a non-hormonal IUD; and hormonal contraception. Because the goal of this study is to characterize nucleotide concentrations within an individual during high and low estradiol exposure, only hormonal contraception options that do not impede cycle fluctuation will be allowed. Estradiol has been well characterized in women taking traditional 21/7 hormonal contraception regimens that allow for monthly menses. While peak estradiol concentrations are slightly diminished (1.6-1.8 fold) after initiating this contraceptive regimen, estradiol's overall concentration vs time profile follows a predictable pattern similar to the pre-contraception pattern. Furthermore, peak estradiol concentrations are still 6-9 fold greater than trough concentrations during these contraceptive cycles. Therefore, we will include women utilizing a traditional 21/7 hormonal contraception regimen in this study. Since estradiol fluctuations over the contraceptive cycle are dramatically reduced by shortening the on/off interval to 23/5 days, women utilizing continuous hormonal contraception options such as Seasonique, injectables, implants, and hormonal IUDs will be excluded from this study.

Pregnancy-related data will be collected using the pregnancy CRFs for all pregnancies detected during the study. After the participant's follow-up study visit, the study team will make every attempt to follow the participant until an outcome of the pregnancy can be ascertained to allow reporting of these outcomes meeting EAE criteria. Pregnancy outcomes that meet criteria for EAE reporting as described above

(e.g., maternal complications, congenital anomalies) occurring among participants known to be pregnant at the Final Study Visit will continue to be expeditiously reported.

#### 14.8 Social Harms Reporting

Although study sites make every effort to protect participant privacy and confidentiality, it is possible that participants' involvement in the study could become known to others, and that social harms may result (i.e., because participants could become known as HIV-infected or at "high risk" for HIV infection). For example, participants could be treated unfairly or discriminated against, or could have problems being accepted by their families and/or communities. Social harms that are judged by the Investigator of Record to be serious or unexpected will be reported to the IRB at least annually, or according to their individual requirements. In the event that a participant reports social harm, every effort will be made by study staff to provide appropriate care and counseling to the participant, and/or referral to appropriate resources for the safety of the participant as needed. While maintaining participant confidentiality, study sites may engage their CABs in exploring the social context surrounding instances of social harm.

### 15. Clinical Management

In general, the site investigator has the discretion to discontinue study product use/participation at any time if they feel that continued product use would be harmful to the participant or interfere with treatment deemed clinically necessary. Unless otherwise specified below, the investigator should immediately consult the PSRT for further guidance regarding permanent discontinuation.

The site investigator or designee will document all discontinuations on applicable case report forms.

### 15.1 Dose Modification Instructions

Study dose will not be modified.

### 15.2 Discontinuation of Study Product in the Presence of Toxicity

Stopping rules have been created to protect the health and safety of study participants. If a single subject experiences a Serious Adverse Event, enrollment will be held while the protocol undergoes review. If 2 or more participants experience Grade 3 or Grade 4 adverse events, enrollment will be held while the protocol undergoes review.

Any Grade 3 or 4 or serious adverse event related to a study intervention (blood draw, biopsy) or the study drug will result in subject discontinuation. Participants who are withdrawn for safety reasons will complete a follow-up visit within 14 days the last sample collection visit.

### 15.3 Pregnancy

Pregnant and lactating women are excluded from this study. Routine serum pregnancy testing is being performed at the screening visit and routine urine testing is being performed at other study visits as noted. If a participant becomes pregnant at any time during the course of the study, study treatment and interventions would be terminated, but she will continue with follow-up visits and safety lab assessments.

Pregnancy-related data will be collected using the Antiretroviral Pregnancy Registry forms for all pregnancies detected during the study. The study team will make a very strong attempt to maintain contact with the pregnant participant until the outcome of the pregnancy is determined or it becomes clear that it will be impossible to obtain outcome information.

## 15.4 Criteria for Early Termination of Study Participation

Participants may voluntarily withdraw from the study for any reason at any time. The site investigator also may withdraw participants from the study to protect their safety and/or if they are unwilling or unable to comply with required study procedures, after consultation with the PSRT. Participants also may be withdrawn if the study sponsors, government or regulatory authorities (including the Office of Human Research Protections), or site IRBs terminate the study prior to its planned end date. Every reasonable effort is made to complete a final evaluation of participants who withdraw or are withdrawn from the study prior to completing follow-up. Study staff members will record the reason(s) for all withdrawals in participants' study records.

## 16. Statistical Consideration

[figure not shown]
### 16.1 Statistical analysis.

*We hypothesize that PrEP nucleotide concentrations in total rectal cells obtained via cytobrush will significantly correlate with isolated CD4+ T cells regardless of estradiol exposure.* To test this hypothesis TFVdp and dATP concentrations in total rectal cells collected by cytobrush at each visit will be compared to CD4+ T cells isolated from rectal biopsies using Pearson's correlation. We expect strong correlations ( $>0.8$ ) to exist during both visits. Linear regression will be performed for log10 concentrations of total rectal cells (X) vs isolated CD4+ T cells (Y) to describe the relationship between these sampling matrices within each visit. These analyses will also be performed for FTCtp and dCTP.

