## 5. Protocol Summary

Protocol Chair:	[name], MS
Sample Size:	10 cisgender females
Study Population:	Premenopausal healthy volunteer cisgender women between 18-49 years of age with an intact gastrointestinal tract
Study Site(s):	NC TraCS Clinical Translational Research Center at the University of North Carolina, Chapel Hill, NC USA
Study Design:	Single-center, open-label PK sampling study
Study Duration:	Women will be enrolled in the study within 42 days of screening, depending on the timing of their menstrual cycle, and then will be on active study for two weeks. A follow-up visit will occur within 14 days.
Study Products:	Truvada®
Study Regimen:	Five witnessed doses daily prior to each sampling visit
Primary Objectives:	To assess the impact of high and low in vivo estradiol exposure on PrEP nucleotide concentrations in different cellular populations of the lower GI tract
Hypothesis:	PrEP nucleotide concentrations in total rectal cells collected via cytobrush will significantly correlate with concentrations in CD4 + T cells isolated from rectal tissue biopsies regardless of in vivo estradiol exposure.
Secondary Objectives:	
To quantify the relationship between estradiol, progesterone and testosterone on PrEP nucleotide concentrations in rectal and peripheral blood mononuclear cells
 
To quantify the relationship between estradiol, progesterone and testosterone on PrEP concentrations in plasma

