## 7. Key Roles

### 7.1 Protocol identification

**Protocol title:** Quantification of Estradiol's Impact on Nucleotides in Different Cellular Populations of the Lower Gastrointestinal Tract

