**Female sex steroid hormones may disproportionately impact PrEP pharmacology in different cellular populations.** Previously, investigators have utilized several different sampling strategies from which to draw conclusions about PrEP pharmacology in HIV transmission sites. These surrogate measures include 1) collecting biopsies for measurement in isolated CD4+ T cells – generally considered gold standard; 2) tissue homogenization for measurement in mixed cell populations; 3) collecting swabs and cytobrush for measurement in fluid or mixed cell populations. A previous clinical study noted a predictive relationship between parent TFV measured in rectal fluids versus tissue homogenates in individuals taking oral TDF. Additionally, Yang et al. demonstrated a predictive correlation between TFVdp in mixed cell populations of homogenized rectal tissue vs CD4+ T cells isolated from rectal tissue following topical application of TFV gel. Yet the impact of estradiol on these surrogate relationships has not been well characterized. One *in vitro* study utilizing very high concentrations of TFV (1mg/ml) suggests that estradiol could disproportionately impact TFVdp formation in epithelial cells (enhanced formation) vs CD4+ T cells (diminished formation), which could confound the relationship between surrogate measures of mixed vs isolated cell populations.

**We aim to quantify estradiol's impact on PrEP nucleotide concentrations in mixed cell populations obtained via cytobrush sampling vs CD4+ T cells isolated from rectal tissue biopsies** in order to understand whether cytobrush is a valid PrEP pharmacology surrogate in people taking exogenous estradiol.

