## 9. Study Objectives

### 9.1 Primary Objective:

To assess the impact of high and low *in vivo* estradiol exposure on PrEP nucleotide concentrations in different cellular populations of the lower GI tract

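### The primary objective asks for the effect of high versus low estradiol, but no between-visit contrast is planned to estimate or test it

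*Combined protocol and SAP*

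**What the plan says.** Four places set the question as an effect of estradiol on concentrations:

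- Section 7.1 titles the study "Quantification of Estradiol's Impact on Nucleotides in Different Cellular Populations of the Lower Gastrointestinal Tract".
- Section 8 states "We aim to quantify estradiol's impact on PrEP nucleotide concentrations in mixed cell populations obtained via cytobrush sampling" versus CD4+ T cells from biopsies, "in order to understand whether cytobrush is a valid PrEP pharmacology surrogate in people taking exogenous estradiol".
- Section 9.1 makes the primary objective the impact of high and low "estradiol exposure on PrEP nucleotide concentrations in different cellular populations of the lower GI tract".
- Section 14.7 says "the goal of this study is to characterize nucleotide concentrations within an individual during high and low estradiol exposure".

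Section 10.5 defines the primary endpoints (TFVdp, FTCtp, dATP and dCTP in cytobrush cells and in rectal CD4+ T cells) at both the low- and high-estradiol phases. Table 1 shows the measurements as matched across Visits 1 and 2.

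The hypothesis under the primary objective in Section 5 is narrower: "PrEP nucleotide concentrations in total rectal cells collected via cytobrush will significantly correlate with concentrations in" CD4+ T cells, whatever the estradiol exposure.

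Section 16.1 contains two analyses. In the first, "TFVdp and dATP concentrations in total rectal cells collected by cytobrush at each visit will be compared to CD4+ T cells isolated" from biopsies by Pearson correlation, with values above 0.8 expected at both visits. In the second, log10 CD4+ concentration is regressed on log10 cytobrush concentration "to describe the relationship between these sampling matrices within each visit". Both are repeated for FTCtp and dCTP. Section 16.2 powers the correlation only: 10 women give 80% power if r exceeds 0.78. Section 17.2 covers bioanalysis.

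**The concern.** The analysis answers whether cytobrush and CD4+ concentrations rank women similarly at each visit. The objective asks whether concentrations change between low and high estradiol, and whether they change differently in the two cell populations. Section 16.1 has no paired comparison, no model with a visit or estradiol term, and no comparison of correlations, slopes or intercepts between visits.

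This matters because of the protocol's own rationale. Section 8 cites in vitro evidence that estradiol may raise TFVdp formation in epithelial cells and lower it in CD4+ T cells, which would distort the surrogate relationship. A correlation is unchanged when either matrix is multiplied by a constant, so it cannot see such an effect if it is similar in every woman. The study could report two significant correlations and conclude that cytobrush is a valid surrogate regardless of estradiol, while a given cytobrush value corresponds to different CD4+ concentrations at the two visits.

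**Working it through.** **The plan's own figure.** The calculation in R's pwr package, recoded for n=10, r=0.78 and two-sided alpha 0.05, gives 81.9% power against the stated 80%. The plan's figure therefore reproduces, for one correlation at one visit. Alpha and sidedness are not in the readable text; one-sided 0.05 would give 89.4%, so two-sided 0.05 is the likely setting.

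**Inputs.** n=10 and r=0.78 come from Section 16.2. The documents give no SDs, between-visit correlations or estradiol effects, so these are assumed: log10 SD 0.3 within each matrix, between-visit correlation ρ of 0 and 0.5, and 40,000 simulated trials per scenario. Two-sided significance at n=10 requires r > 0.632.

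**Case (a): estradiol multiplies the cytobrush:CD4+ ratio by a similar factor in every woman.**

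| Uniform ratio shift | Both correlations significant, ρ=0 | ρ=0.5 | Median slope |
|---|---|---|---|
| none | 70.0% | 71.1% | 0.78 |
| 2-fold | 69.7% | 71.1% | 0.78 |
| 4-fold | 69.8% | 71.1% | 0.78 |

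The level depends on the setting (82-83% at one-sided 0.05, 56-58% with raw concentrations, 88-89% if r is 0.85); it does not depend on the shift.

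The SD of the paired change in log10(cytobrush:CD4+) is SD × √[4(1−r)(1−ρ)]:

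- ρ=0: 0.3 × √(4 × 0.22) = 0.281. A 2-fold change (0.301) is 1.07 SD, with 85% power.
- ρ=0.5: 0.3 × √(4 × 0.22 × 0.5) = 0.199. A 2-fold change is 1.51 SD, with 99% power.

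The rejection rate with no shift is 5%.

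The shift does reach the regression intercept. The intercept change is (shift in Y) − 0.78 × (shift in X), so a 2-fold ratio shift moves it by 0.23 log10 (X only) to 0.30 (Y only). With no shift at all, the between-visit intercept difference has a sampling SD of 0.07-0.09, 0.31-0.35 or 0.60-0.68 when mean log10 cytobrush concentration is 0, 1 or 2. Comparing the two intercepts by eye is therefore unreliable unless X is centred near zero.

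**Case (b): estradiol changes both matrices 2-fold.** The intercept moves (1 − 0.78) × 0.301 = 0.07 log10, although the concentration effect named in Section 9.1 is present in full.

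**Case (c): the effect varies between women (SD 0.2 to 0.4 log10, ρ=0.5).** If one matrix is affected, median Visit 2 r falls to 0.67-0.49 and both-visit significance to 50-25%. If the effect is split in opposite directions across the two matrices, the figures are 0.63-0.24 and 42-8%. The planned correlation responds, but no step attributes the fall to estradiol.

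**What 10 pairs can deliver.** From the noncentral t distribution, 80% power at two-sided 0.05 needs a mean change of 0.996 SD of the paired log10 change. The detectable fold is 10^(0.996 × SD), and the 95% CI factor is 10^(2.262 × SD/√10).

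| SD of paired log10 change | Detectable fold | 95% CI: estimate ×/÷ |
|---|---|---|
| 0.2 | 1.6 | 1.4 |
| 0.3 | 2.0 | 1.6 |
| 0.4 | 2.5 | 1.9 |
| 0.5 | 3.1 | 2.3 |

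**The case against.** The best defence is that the objective is made operational through the hypothesis. Section 5 puts the correlation hypothesis directly beneath it, Section 8 gives surrogate validity as the purpose, and Sections 16.1 and 16.2 test and power exactly that. This explains the correlations, and they should stay. It does not supply what the title, Section 9.1 and Section 14.7 ask for, which is a change in concentration within a woman.

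It is also true that each visit's regression will be reported, so a uniform ratio shift would show in the intercepts, and that a variable effect would lower Visit 2 r. Neither is compared between visits, and neither measures a change in concentration.

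Several technical points stand as limits:

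- The 85-99% power applies to the ratio contrast at SD 0.3. The within-matrix change, which is closer to Section 9.1, has SD 0.3 × √[2(1−ρ)] = 0.42 to 0.30, so power for a 2-fold change is 52-81%. At SD 0.5 the two contrasts have 44-72% and 23-40%.
- In case (c) the fall in r depends on the spread of the effect between women; the size of the mean effect plays no part.
- The change in log ratio equals a change in calibration only if the slope is 1.
- Visit is a proxy for estradiol. Section 10.1 only predicts the levels, and Section 14.7 admits 21/7 contraceptive users with lower peaks.
- Replacement secures complete sampling, but values below the quantification limit could still leave fewer than 10 pairs.

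These argue for estimation with stated precision. They do not argue for leaving the contrast out.

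**Conclusion.** The concern holds. The stated hypothesis has a specified and adequately powered test at each visit; the estradiol effect in the title and primary objective has no estimate and no test. That gap is a matter of text and rests on no assumption. Its consequence follows from the algebra of correlation: a uniform shift of any size leaves both correlations unchanged, so both are significant in 70-71% of trials at 1-, 2- or 4-fold. The power of the paired contrasts and the width of their intervals do rest on assumed SDs and between-visit correlations, which is why ranges are given. This should be corrected before analysis, because following the plan as written leaves the primary objective unanswered and could support a misleading claim of validity regardless of estradiol.

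**What to change.** In Section 16.1, keep the per-visit correlations, report each with a 95% CI, and state alpha and sidedness. Add, for each nucleotide on the log10 scale:

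1. the within-woman geometric mean Visit 2/Visit 1 ratio in cytobrush cells and, separately, in CD4+ T cells;
2. the paired change in log10(cytobrush:CD4+).

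Give each a 95% CI and designate them as the analysis of the primary objective. This makes 4 nucleotides × 3 contrasts = 12 estimates. Report them as estimation with unadjusted intervals, labelled as such, with TFVdp and dATP first, and give the number of quantifiable pairs behind each. Show the serum estradiol already measured at both visits alongside, so that the reader can see whether exposure rose.

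State also that:

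- the visit contrast is confounded with the fixed visit order and the second five-dose course;
- independence from estradiol will not be concluded from two significant correlations alone;
- with 10 pairs, 80% power at two-sided 0.05 needs a mean change of about 1.0 SD of the paired log10 change.

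The cost is an addition to the analysis plan and a little more analysis. Matched samples from 10 evaluable women are already planned, and unevaluable women are replaced (Section 16.3), so no extra women, visits or samples are needed. The price is that some intervals may be wide.

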## 10.4 Study Sampling

At both sampling visits, the following samples will be collected in all participants:

1. Blood plasma
2. Serum

3. PBMCs
4. Rectal tissue biopsies
5. Rectal cell collection by cytobrush

10.5 Primary Endpoints:

TFVdp, FTCtp, dATP and dCTP concentrations in mixed rectal cells collected via cytobrush vs CD4+ T cells isolated from rectal tissue biopsies during the early (low estradiol) and late (high estradiol) follicular phases of the menstrual cycle

10.6 Secondary Endpoints:

1. Estradiol, progesterone and testosterone concentrations in serum
2. TFVdp, FTCtp, dATP and dCTP concentrations in peripheral blood mononuclear cells
3. TFV and FTC concentrations in plasma

Table 1 Sample collection and bioanalytical measurement

Matched Visit 1 and 2 Measurements	
Collection Matrix	Bioanalytical assay
PBMCs	TFVdp FTCtp dATP dCTP
Total rectal cells	TFVdp FTCtp dATP dCTP
Rectal CD4 cells	TFVdp FTCtp dATP dCTP
Plasma	TFV FTC
Serum	Estradiol progesterone testosterone
TFVdp=tenofovir diphosphate; FTCtp=emtricitabine triphosphate; dATP=deoxyadenosine triphosphate; dCTP=deoxycytidine triphosphate; TFV=tenofovir; FTC=emtricitabine	

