### 16.2 Sample Size and Power Calculations

Power determination for the correlation analysis was carried out using the R-package pwr. This package

Figure 4 Power Determination

Sample size required to detect a positive correlation given various scenarios of r and beta values.

implements the power calculation methods described in Cohen, 1988. Assuming r is >0.78, a sample size of 10 women achieves 80% power (Figure 2). This assumed r value is more conservative than our previous observation of TFV concentration in rectal fluid versus tissue homogenate where r was 0.944.

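### The cytobrush–CD4+ relationship is analysed at each visit alone and the visits are never compared, although the hypothesis is that it holds whatever the estradiol level

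*Combined protocol and SAP*

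**What the plan says.** Section 16.1 states the hypothesis that nucleotide concentrations in cytobrush cells correlate significantly with those in CD4+ T cells at any estradiol exposure. To test it, cytobrush concentrations "at each visit will be compared to CD4+ T cells isolated from rectal biopsies using Pearson's correlation". Strong correlations, above 0.8, are expected "to exist during both visits". The log10 regression of CD4+ on cytobrush is meant "to describe the relationship between these sampling matrices within each visit".

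Section 16.2 reads: "Assuming r is >0.78, a sample size of 10 women achieves 80% power". The method is a single-correlation calculation in the R package pwr.

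Section 10.4 has both rectal samples taken from all participants at both visits, and Table 1 is headed "Matched Visit 1 and 2 Measurements". Section 14.7 describes the aim as a within-woman comparison of high and low estradiol. Section 16 contains no repeated-measures model, common slope, visit-by-cytobrush interaction or other estimate of the difference between visits.

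**The concern.** The question is whether estradiol changes how well cytobrush cells stand in for CD4+ cells. The planned output is two correlations, two regressions and two sets of p-values, with nothing that sets one visit against the other. If one visit reaches significance and the other does not, the plan has no rule for reading the result. The obvious reading, that estradiol breaks the relationship, may be wrong, because such a split arises often when the true correlation is the same at both visits. The plan also leaves unused the fact that the same 10 women supply both sets of pairs. Information is scarce here: there are 20 biopsy visits in all.

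**Working it through.** **Inputs.** From Section 16.2: 10 women, r = 0.78, 80% power, pwr method. From Section 10.4 and Table 1: two pairs per woman, hence 20 pairs. Sections 11.2 and 16.3 replace unevaluable women, so no loss is assumed. Two inputs are assumptions. The readable text gives no alpha (Figure 4 is not shown), so two-sided 0.05 is used. The between-visit correlation w, applied to both the cytobrush values and the residuals, is not given anywhere, so a range is shown.

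**Step 1: the plan's own figure.**
- Critical r = t/√(t² + n − 2), with t = 2.306 on 8 df: 2.306/√(5.318 + 8) = 0.632. Its Fisher z is 0.745.
- z for r = 0.78 with the pwr bias term r/(2(n − 1)): 1.045 + 0.78/18 = 1.089.
- Power = Φ[(1.089 − 0.745) × √7] = Φ(0.910) = 81.9%.

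The r that gives exactly 80% is 0.770. One-sided 0.05 gives 89.4% and two-sided 0.025 gives 72.6%, so neither reproduces the figure. The stated 80% is right, and it is the power of one visit's test.

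**Step 2: what two separate tests give when nothing differs.** Simulation with true r = 0.78 at both visits, 3,000 trials per row, Monte Carlo error about 1 point:

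| w | a given visit significant | both significant | exactly one = 2 × (given − both) |
|---|---|---|---|
| 0 | 83.5% | 70.1% | 26.8% |
| 0.5 | 83.6% | 71.3% | 24.6% |
| 0.7 | 83.3% | 72.7% | 21.2% |
| 0.9 | 83.1% | 76.9% | 12.4% |

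As a check at w = 0: 0.835² = 69.7% for both, and 2 × 0.835 × 0.165 = 27.6% for exactly one. A separate set of runs gave exactly one in about 26% at w = 0.5 and about 10–28% for w from 0.95 to 0, and both in about 69–78%.

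**Step 3: how precise a comparison can be.**
- At one visit with observed r = 0.78, the 95% CI on the z scale is 1.045 ± 1.96/√7 = 1.045 ± 0.741, or r from 0.30 to 0.95.
- For the difference of two z values at w = 0, the half-width is 1.96 × √(1/7 + 1/7) = 1.05. That is about the distance from r = 0.78 (z = 1.045) to r = 0.

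This is a guide on the correlation scale, not the interval for a slope, and positive w narrows it. It shows both why two p-values say little about a difference and why any estimate of the difference will be wide.

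**Step 4: a joint test of a common association.** Each woman's two CD4+ values are permuted together; the statistic is the sum of the two within-visit correlations. Power for w from 0.95 to 0:
- r = 0.7: about 68% for one visit, 72–93% jointly.
- r = 0.78: about 83% for one visit, 85–98% jointly.

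At r = 0.6 the joint test reaches 60–75% for w from 0.8 to 0, against 48–50% for one visit. In a similar permutation test using Fisher z, rejection at r = 0 was about 5%.

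**Step 5: what the joint test cannot show.** Its null is no association at either visit, so an association at one visit can reject it. With r = 0.8 at one visit and 0 at the other, it was significant in about 22–38% of trials, while both per-visit tests were significant in 3–5%. Other joint statistics were no safer (w = 0.7 and 0.3): 34–37% for a random-intercept model with 8 df, and 48–58% for a permutation test of the mean Fisher z.

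**The case against.** The per-visit layout follows from the hypothesis. A claim that the correlation holds at low and at high estradiol needs evidence at each level, and an average association is a weaker claim. Each per-visit test uses one pair per woman, so it needs no independence between visits, and it has the power stated. If r exceeds 0.8, as the plan expects, power at one visit is at least about 85%. The plan cites an earlier r of 0.944, though for parent drug in rectal fluid against tissue homogenate. Nothing in the documents says that a split result would be read as an estradiol effect.

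All of this stands, and it rules out several stronger readings:
- **The per-visit tests are invalid, or the sample size is wrong.** Step 1 shows otherwise, and the plan never treats 20 pairs as independent.
- **Half of the information is lost.** That is exact only at w = 0. At w = 0.95 the joint test gains only a few points, and the documents do not exclude a high w in the same women about ten days apart.
- **The joint test should replace the per-visit tests.** Step 5 shows that it can succeed when the relationship is absent at one estradiol level. It does not rescue a low correlation either: at r = 0.6 it stays below 80%.

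What the objection leaves untouched is that two p-values do not estimate a difference, and the plan offers nothing else.

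**Conclusion.** This is a gap in the analysis, not an error in the tests that are planned. Section 16.1 never compares the two visits, although that comparison is what the hypothesis turns on. If r is 0.78 at both visits, a split result has roughly a one-in-four chance at w = 0.5 (about 10–28% over the range), and the chance of significance at both is about 69–78%, below the 80% that applies to one visit. These figures rest on two-sided 0.05, bivariate normal log10 values, equal r at both visits and an assumed w.

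A model of the 20 pairs supplies the missing estimate. Visit order is fixed by Section 10.1, so the visit contrast stands for estradiol only as far as nothing else that matters differs between the first and second visit. A wide interval for the slope difference would show how little 10 women can settle, which is more honest than leaving two p-values to be compared by eye.

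**What to change.** In Section 16.1:
1. Keep the Pearson correlations at each visit as the assessment at low and high estradiol, and report each with a 95% CI.
2. Add one repeated-measures analysis of all 20 log10 pairs: CD4+ on cytobrush, visit as a factor, visit-by-cytobrush interaction, woman as the unit.
3. Report the between-visit slope difference with its 95% CI as the direct estimate of estradiol's influence on the relationship.
4. Specify a small-sample method. For the common association, permute each woman's two CD4+ values together. If a mixed model is used, fix the degrees of freedom in advance: for the common slope, a naive 17 df gave 7–9% type I error in simulation, and 8 df gave about 5–6%.
5. Label the common-association test supportive, and say that it cannot by itself show that the relationship holds at both estradiol levels.
6. State that significance at one visit only is not evidence of an estradiol effect.

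The cost is a paragraph of plan text and a little more analysis work, with no extra women, visits or samples. The drawback is an imprecise slope difference, which the plan should acknowledge in advance.
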